## **5.2 Statistical Methods**

We will compare primary and secondary outcomes in the Plan and Pledge arm to the Usual Care, “Promote” arm using 2-tailed chi-squared tests as well as logistic regression analyses. Analyses will adjust for correlation of outcomes within clusters. We hypothesize that a higher proportion of participants in the Plan and Pledge arm will report their self-test results than in the Usual Care arm, “Promote”.

### **5.2.1 Analysis of Primary Outcome**

Our primary outcome is the reporting self-test usage, measured by the percent of self-test recipients reporting use of HIV self-test kits to dedicated WhatsApp number by arm and compared to the standard of care arm of the STAR program

### **5.2.2 Analysis of Secondary Outcome(s)**

1) The percent of self-test recipients who consent to phone/SMS follow-up by study arm and compared to the standard of care arm of the STAR program. 2) The percent of self-test recipients who are successfully reached for follow-up by phone about 7 days after receiving the HIV self-test, by study arm and compared to the standard of care arm of the STAR program, 3) The percent of self-test recipients who report self-test result on the dedicated WhatsApp number and are HIV positive, by study arm and compared to the standard of care arm of the STAR program. 4) The Ratio of negative:positive test results reported by study arm and compared to the standard of care arm of the STAR program.. 5) Percent of on-site testers by study arm and compared to the standard of care arm of the STAR program. 6) The percent of self-test recipients who seek confirmatory testing by study arm and compared to the standard of care arm of the STAR program

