In the context of the STAR program that is distributing HIV self-tests in South Africa, one of the desired outcomes is that individuals who obtain a self-test kit at distribution sites go on to take the test either immediately on site or in the near future at their home. A second desired outcome is that after using the self-test kit, individuals who use self-tests will report their results to a WhatsApp number that has been established for this purpose. A third desired outcome is that individuals who obtain a reactive test result will seek a confirmatory test at local clinics that provide HIV testing and counseling services. Those with a confirmed HIV-positive test result can be encouraged to seek HIV care, which includes treatment with antiretroviral therapy (ART). This pilot project will test whether commitment and planning prompts administered at the time of self-tests distribution are effective in promoting the desired behaviors.

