### **3.3 Study Measures**

The study will be implemented by WRHI. UPenn will only partake in the design and the analysis of de-identified aggregate data. As such, all study procedures will be conducted by the WRHI team and reviewed by the University of Witwatersrand IRB. WHRI will share any modifications submitted to Witwatersrand IRB with the UPenn team, and the UPenn team will share these documents with UPenn IRB according to the specific requirements and procedures of the UPenn IRB.

During distribution of the self-tests, an intake form will be completed (a copy of this form can be found in the attached STAR SOP). This form will track the self-test recipient's arm assignment, on-site or off-site testing, and consent for follow-up phone call.

If a self-test recipient messages the WhatsApp number or receive a follow-up call, they will be asked the following series of questions (questions are sequential and continuation of questions is dependent on response to previous question): Did they use self-test? What is their test result? (if they are willing to share), Would like a confirmatory test? Did they attended confirmatory testing? What was the confirmatory test result? Would they want to be linked to care? What date were they linked to care? ART initiation? Date of ART initiation? Linked to VMMC? Date of VMMC?

As outlined in the attached STAR WhatsApp card, all text messages are confidential and de-identified. Data tracking record keeping is also de-identified with only the HIV self-test kit bar code recorded.

Please see section 5 Statistical Plan for outcomes and analysis.

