## **STUDY POPULATION AND DURATION OF PARTICIPATION**

### **3.4 Duration of Study Participation**

The intervention will be implemented at the time of HIV self-test distribution and there is no follow-up period. Participants are instructed to use the HIV self-test at home and complete the Plan and Pledge form whenever they choose. If the participants opts to test on-site, they can complete the Plan and Pledge on-site as well. Participants are asked during distribution if they would like to receive a follow-up call, as part of standard procedures with the STAR program. Follow-up calls will be made by the WRHI team about 5 days after distribution. Follow-up calls may include, if the individual used the HIV self-test, if they are willing to share their test result, and questions about the Plan and Pledge intervention, such as if the individual completed the Pledge and Plan cards.

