## **5. STATISTICAL PLAN**

### **5.1 Sample Size and Power Determination**

To detect a difference in the primary outcome of 5% percentage points (from 2.5% reporting to 7.5% reporting) with 80% power and at alpha = .05, with rho=.01 and cluster size per day = 30 per arm, we plan to recruit 660 participants per arm with a total of 1,320 participants.

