### **9.4 Informed Consent Process**

We are asking for a waiver in consent. As outlined in section 5.1 and 5.4, involvement in the study will be voluntary. Participation will be opt-in and it is likely that the act of providing informed consent will influence the effect of the interventions and outcomes in the usual care group.

Study consent procedures will follow the approved STAR program protocol in which self-test recipients provide verbal consent to receiving follow-up calls to ascertain whether they used self-tests and self-test results.

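### Secondary outcome 6 counts confirmatory testing over all recipients but, on the visible text, is observed only in people who message or are called, so it mixes behaviour with ascertainment that can differ by arm

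*Combined protocol and SAP*

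**What the plan says.** Section 5.2.2 lists as outcome 6 "The percent of self-test recipients who seek confirmatory testing by study arm". Section 2.2 words the matching objective as behaviour: the effect of the prompts on the likelihood of seeking confirmatory testing.

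Section 3.3 gives the only visible source: "If a self-test recipient messages the WhatsApp number or receive a follow-up call, they will be asked the following series of questions". The series includes "Would like a confirmatory test? Did they attended confirmatory testing", and each question depends on the answer before it. The intake form, completed at distribution, tracks arm, on-site or off-site testing, and agreement to a call. It is not said to record confirmatory testing. Records carry only the kit bar code, and no link to clinic records is described. No rule says how people who are never heard from are to be counted.

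Section 5.1 plans the primary outcome, WhatsApp reporting, to move "from 2.5% reporting to 7.5% reporting" with 660 recipients per arm. Section 5.2.2 also makes call consent and phone reach outcomes compared by arm. Section 4 refers study procedures to the STAR protocol and SOP, which are attachments not reproduced here.

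**The concern.** An all-recipient denominator with answers from only some recipients sets everyone else to no. That would be harmless for the ratio between arms if the chance of being heard from were the same in both. Here one of the two channels is the behaviour that the intervention is meant to change, and access to the other depends on consent and reach, which are themselves outcomes. If the prompt made people message more and changed nothing else, outcome 6 could still differ between arms, and the objective in section 2.2 would invite reading that as an effect on seeking confirmatory testing.

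Part of an effect that runs through WhatsApp could be real, because the scripts in section 3.1 present reporting as a way to obtain support. Outcome 6 alone cannot separate that part from better ascertainment.

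**Working it through.** The plan states no figure for outcome 6, so there is none to reproduce.

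**Inputs from section 5.1:** WhatsApp reporting w = 0.025 (Usual Care) and 0.075 (Plan and Pledge); 660 per arm.

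**Assumed, because the documents give no values:** phone reach among non-messagers, q = 10%, 30%, 50%; true confirmatory-testing rate c = 1% to 10%, equal in both arms. Low values of c are plausible because section 1 describes this step as one where "individuals who obtain a reactive test result will seek a confirmatory test at local clinics".

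**Further assumptions:** w applies to people who seek confirmatory testing as it does to all recipients; every message or call yields the answer; and, given arm, being heard from is unrelated to having sought a test.

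**Share heard from:** s = w + (1 − w)q. The observed rate is c × s, so the ratio with no true effect is s1/s0 (1 = Plan and Pledge, 0 = Usual Care).

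| q, both arms | s0 | s1 | Ratio |
|---|---|---|---|
| 10% | 0.025 + 0.975 × 0.10 = 0.1225 | 0.075 + 0.925 × 0.10 = 0.1675 | 1.37 |
| 30% | 0.025 + 0.975 × 0.30 = 0.3175 | 0.075 + 0.925 × 0.30 = 0.3525 | 1.11 |
| 50% | 0.025 + 0.975 × 0.50 = 0.5125 | 0.075 + 0.925 × 0.50 = 0.5375 | 1.05 |

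At q = 100% the ratio is 1.00. The value 0.075/0.025 = 3.0 is only the limit if calls supply no answers.

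**In people.** At c = 2.5% and q = 30%, the expected counts are 660 × 0.025 × 0.3175 = 5.2 and 660 × 0.025 × 0.3525 = 5.8, or 0.79% against 0.88%.

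**Unequal reach.**
- 30% against 40% (Usual Care, Plan and Pledge): 0.3175 and 0.445, ratio 1.40.
- 40% against 30%: 0.415 and 0.3525, ratio 0.85.
- The bias cancels when Plan and Pledge reach is (s0 − 0.075)/0.925 = 5.1%, 26.2% or 47.3%. That is 4.9, 3.8 or 2.7 points below a Usual Care reach of 10%, 30% or 50%. Beyond that it reverses.

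**Equal overall reach does not fix the direction.** Let r be reach among all recipients and f the share of messagers who are also reached, so s = r + w(1 − f). With r = 0.3 in both arms:
- f = 0.3 and 0.9: 0.3 + 0.025 × 0.7 = 0.3175 and 0.3 + 0.075 × 0.1 = 0.3075, ratio 0.97.
- f = 0 and 1: 0.325 and 0.300, ratio 0.92.

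The condition must therefore be on reach among non-messagers. For the same reason, the reporting and reach percentages already planned do not give the share heard from. At r = 0.3 it can lie anywhere from 0.300 to 0.325 in Usual Care and from 0.300 to 0.375 in Plan and Pledge.

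**Chance of p < 0.05 with no true effect** (exact binomial enumeration of the uncorrected two-sided chi-squared test, 660 per arm, clustering ignored, equal q):

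| c | q = 10% | q = 30% | q = 50% |
|---|---|---|---|
| 1% | 1.5% | 4.5% | 4.6% |
| 2.5% | 5.6% | 4.6% | 5.0% |
| 5% | 6.6% | 5.8% | 5.2% |
| 10% | 10.4% | 6.5% | 5.5% |

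**Sensitivity analysis.** Suppose the rate in those not heard from is k times the rate in those heard from. The ratio becomes (s1 + (1 − s1)k)/(s0 + (1 − s0)k). For k = 0, 0.25, 0.5 and 1:
- equal reach of 30%: 1.11, 1.05, 1.03, 1.00
- 30% against 40%: 1.40, 1.20, 1.10, 1.00
- 40% against 30%: 0.85, 0.92, 0.96, 1.00

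The plan as written corresponds to k = 0.

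**The case against.** **Direction.** A reader might infer that the plan favours Plan and Pledge whenever phone reach is equal. The documents do not support that. As shown above, equal overall reach with different overlap can give 0.97 or 0.92. The 2.5% and 7.5% are also rates for all recipients; nothing says that the threefold gap holds among the few who seek a confirmatory test, and if messaging is equal in that group there is no bias at equal reach. This objection stands, and it limits the directional claim to the stated conditions.

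**Completeness of messages.** The script asks people to report after the screening test. A message sent at once may answer whether a confirmatory test is wanted, but not yet whether it was attended. Section 3.3 does not say when each question is put, so the WhatsApp contribution may be overstated in the ratios above.

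**Unseen source.** The STAR protocol or SOP may name another source for confirmatory testing. This stands, and the point is made on the visible text only.

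**Already visible, and small.** Reporting, consent and reach are already compared by arm, and at 2.5% and 30% reach the shift is less than one person per arm. The rejection rate there is 4.6%, against 4.3% with equal ascertainment. This supports a minor rating. It does not remove the point: the overlap stays unknown, no reach is stated, and small counts protect the p-value rather than the estimate.

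**Conclusion.** The point holds as a minor one. On the visible text, outcome 6 measures reported confirmatory testing, and its comparison between arms mixes behaviour with ascertainment that may differ by arm.

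The bias is towards Plan and Pledge if three conditions hold: the messaging gap applies to people who seek confirmatory testing, messages yield the answer, and phone reach among non-messagers is equal by arm and below 100%. If any of these fails, the bias can vanish or reverse. The ratios of 1.37, 1.11 and 1.05 illustrate that case only, since reach, overlap and the true rate are all assumed.

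They also describe no true effect. With a real benefit, missing answers can instead shrink the absolute difference. At equal reach among non-messagers this happens once the true risk ratio exceeds 0.975/0.925 = 1.05.

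A reader might infer a serious risk of false-positive findings. In the settings examined with equal reach the rate is mostly near 5%, and it reaches 10.4% only at 10% reach with a true rate of 10%. The problem lies in the estimate and how it is read, for one of six secondary outcomes. The primary outcome is unaffected, because it is itself defined as reporting.

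**What to change.** In section 5.2.2:

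1. Name the question and channel that define outcome 6, label it 'reported confirmatory testing', and state that a difference will not by itself be read as an effect on behaviour.
2. Report by arm the percent of recipients heard from by WhatsApp only, call only, both, and either. Request the data in that form now, because under section 7 the analysis team receives only aggregate data and the overlap may not be recoverable later.
3. Add a short sensitivity analysis with the rate in those not heard from set at 0, 0.25, 0.5 and 1 times the rate in those heard from. A comparison of call answers alone, among those reached, is optional. Mark it as supportive, because consent and reach arise after randomisation and the group is selected.

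If the STAR documents hold a source that does not depend on arm, name it and use that instead.

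Confirm also that calls ask the confirmatory-testing questions. Section 3.3 applies them to calls, whereas section 3.4 mentions use, result and the cards, and section 9.4 says "self-test recipients provide verbal consent to receiving follow-up calls to ascertain whether they used self-tests and self-test results". Neither list claims to be complete.

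**Cost:** wording, one table, a data request split by channel and arm, and a weaker behavioural claim for this outcome. No new data are needed if calls already ask the section 3.3 questions. The call-only comparison would be imprecise: at 30% reach it has 660 × 0.30 = 198 per arm and about 48% power even for 5% against 10%, ignoring clustering.

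A separate drafting point is call timing. Section 3.4 says "Follow-up calls will be made by the WRHI team about 5 days after distribution", while section 5.2.2 counts those "successfully reached for follow-up by phone about 7 days after receiving the HIV self-test", as does section 2.2. These sections should be reconciled.

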## **6. SAFETY AND ADVERSE EVENTS**

The study will be implemented by the WRHI team. UPenn will only partake in the design and the analysis of de-identified aggregate data. As such, any adverse events will be reported by the WRHI team to the University of Witwatersrand IRB, and will be handled according to their specific procedures. WHRI will share any AEs submitted to Witwatersrand IRB with the UPenn team, and the UPenn team will share these documents with UPenn IRB according to the specific requirements and procedures of the UPenn IRB.

## **7. STUDY ADMINISTRATION, DATA HANDLING, AND RECORD KEEPING**

The study will be implemented by the WRHI team. UPenn will only partake in the design and the analysis of aggregate de-identified data. Therefore all study administration, data handling, and record keeping, will be managed by WRHI. WRHI will manage all communications and documentation with the local IRB at the University of Witwatersrand. Any changes to the “Plan and Pledge” pilot will be submitted to the UPenn IRB for review. De-identified aggregate data will be shared with the UPenn team through secure channels (password protected and/or encrypted).

## **8. STUDY MONITORING**

The study will be monitored by the PI and managers at WRHI, as listed on the STAR protocol.

## **9. ETHICAL CONSIDERATIONS**

### **9.1 Risk**

Based on the current and on-going HIV self-test distribution by WRHI and STAR program, we believe that the study is minimal risk. As with any HIV testing research there is the possibility of psychological distress for study participants due to testing. To minimize risk the STAR program diligently follows the HIVST guidelines of South Africa provided by the National Department of Health.

### **9.2 Benefits**

The main direct benefit of this study, is that we will provide free HIV self-testing kits, allowing individuals to know their HIV status in the privacy of their home. Indirectly, the study may give rise to increased identification of HIV-positive persons and increased engagement in HIV care and treatment, thereby reducing the overall number of HIV transmissions occurring as well.

### **9.3 Risk and Benefit Assessment**

We believe that the benefits of this study far outweigh the risks. Given the public health importance of achieving higher uptake of HIV testing among high-risk populations, it is vital to find effective new strategies that can be used to promote testing and identify HIV-positive persons unaware of their HIV infection. The knowledge gained from this study is particularly relevant at a time when countries in Africa are actively developing HIV self-testing policies and seeking optimal ways to scale-up HIV self-tests. Our study will provide data on low-touch, inexpensive nudges, than can be added to currently existing HIVST distribution programs.

### **9.4 Informed Consent Process**

We are asking for a waiver in consent. As outlined in section 5.1 and 5.4, involvement in the study will be voluntary. Participation will be opt-in and it is likely that the act of providing informed consent will influence the effect of the interventions and outcomes in the usual care group.

Study consent procedures will follow the approved STAR program protocol in which self-test recipients provide verbal consent to receiving follow-up calls to ascertain whether they used self-tests and self-test results.

## **10. STUDY FINANCES**

### **10.1 Funding Source**

The STAR program with WRHI is funded by UNITAID and the Gates Foundation. The UPenn pilot is funded by the Gates Foundation, grant number OPP1195218.

### **10.2 Conflict of Interest**

No COI to report. All University of Pennsylvania Investigators will follow the University of Pennsylvania Policy on Conflicts of Interest Related to Research.

## **11. PUBLICATION PLAN**

Findings from this study will be published in peer-reviewed journals and presented at scientific conferences. There is no projected impact on publication or presentation plans.

## **13. ATTACHEMNTS**

1. STAR protocol
2. STAR protocol ethics approval
3. STAR program fixed distribution SOP
4. STAR program WhatsApp card
5. Plan and pledge commitment card
